Hypothesis: Among transgender MAAB persons on csHT who report perfect adherence by iTAB in the past 34 days (ie, two intracellular half-lives) the mean intracellular tenofovir-diphosphate (TFV-DP) concentrations, as measured in DBS, will be equivalent to the levels of perfect adherence previously defined in MSM.

Sub-study I Secondary Objectives

- 1. To determine whether csHT interacts with PrEP in MAAB persons that would affect hormone effectiveness, measured by estrogen concentrations assessed at Weeks 0 and 12 of study follow-up.
 - **Hypothesis**: Among transgender MAAB persons on csHT, estrogen concentrations will not change significantly between baseline (Week 0) and Week 12 in individuals taking PrEP and receiving stable estrogen therapy (controlling for route and formulation).
- 2. To determine TFV-DP in MAAB of all adherence levels compared to not taking csHT, adjusting for confounding factors.
- 3. To determine TFV-DP in MAAB taking versus not taking antiandrogen medications (i.e., spironolactone, finasteride)
- 4. To measure the change in testosterone concentrations between baseline and Week 12 in female-assigned at birth (FAAB) taking PrEP and receiving stable testosterone therapy.
- 5. To determine emtricitabine-triphosphate (FTC-TP) concentrations (a measure of recent adherence) in TG / GNC persons of all adherence levels taking versus not taking hormones.
- 6. To determine changes in desired effects of csHT in TG / GNC persons taking PrEP as measured by the Body Image Scale (BIS).

Sub-study IV Objectives:

- 1. To determine the impact of genital STIs on CVF TFV levels.
- 2. To determine the impact of cytokine mediators of CV inflammation on CVF TFV levels.
- 3. To determine the impact of CV microbiome on CVF TFV levels.

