Ace measured by TFV-DP predicts efficacy in MSM, but similar studies have not yet validated these cut-off points among transgender persons. It is possible that even higher levels of adherence may be needed for other populations. Such studies are necessary because in iPrEx Ole, transgender subjects had 30% lower levels of TFV-DP for reasons that were not determined but could be from poorer adherence, different pharmacokinetics or both (20). Therefore, a cut off for TFV-DP drug levels alone may not accurately address the question of PrEP adherence in the transgender population until similar dose-related TFV-DP levels are confirmed. Additional data is needed on use of hormones by transgender and the levels of TFV-DP and FTC.

Study Rationale

TDF/FTC has been approved by the FDA as an agent for PrEP. As noted previously, little research assesses the uptake and adherence of PrEP in transgender persons. CCTG 603, will implement PrEP at five sites in Southern California (UCSD, Harbor-UCLA, USC, LALGBT and FHCSD) to explore the PrEP use in transgender persons and methods to maintain adherence to drug. CCTG 603 will perform a randomized study of the iTAB+MI-B versus iTAB alone for TDF/FTC adherence for PrEP. This study will test if adherence can be enhanced (and by what degree) over and above personalized daily text reminders by real-time motivational interviewing techniques provided by telephone.

Sub-study II Background

One of the challenges to the use of PrEP in transgender individuals is the concern over the potential interaction of hormone therapy (exogenous estrogen and antiandrogens) with TDF/FTC and subsequent hormone and drug levels. Currently no evidence or clinical studies examine whether drug interactions occur between TDF/FTC and cross-sex hormone therapy (csHT) for gender transition. Concerns about these drug interactions could operate in a bi-directional manner and in our focus group and community consultations there was a particular concern among transgender women taking feminizing hormones. Recent studies examining willingness to take PrEP in transgender women suggest that decreased efficacy of hormone therapy may be a major barrier (90, 91). In the iPrEx open-label extension study, PrEP concentrations in DBS were lower among transgender women with an

adjusted OR of 0.72 (CI 0.55-0.94) (20). While this finding may be accounted for by lower adherence, there are some theoretical reasons for hormones to interact with PrEP.

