The primary outcome is the intracellular TFV-DP levels, as measured in DBS, which is a continuous variable. Comparison between the MAAB and the existing MSM data that will be compared using a two-sample t-test. Differences in the means between the two groups, along with the standard deviations (SD) and their 95% confidence intervals will be reported. As a secondary/sensitivity analysis, multiple regression analysis will be performed to study the association between clinical and demographic factors (age, race, ethnicity, education, socioeconomic status, sexual risk behaviors, substance use, depression, concomitant medications) and group, adjusting for baseline demographic, stratification variables, and clinical characteristics. Variables significantly associated with both group and outcome (p<0.10) will be included in a multiple regression model as covariates.

For the main secondary hypothesis, in MAAB on csHT, to determine the change between baseline and week 12 estradiol levels in individuals taking PrEP and receiving stable estrogen replacement (controlling for route, dose and formulation), we will use a paired t-test. As estradiol concentrations can be unpredictable, we will measure estradiol concentrations in individuals choosing not to initiate PrEP at the same time points. Similar to 3A, multiple regression models will be developed if there are factors that require adjustment in this model.

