Other secondary analyses will explore further interactions between PrEP and csHT in MAAB we will perform analyses of the following potential interactions: a) TFV-DP in transgender persons (MAAB and FAAB) of all adherence levels compared to not taking csHT, b) TFV-DP in MAAB taking versus not taking antiandrogen medications (i.e. spironolactone and finasteride) and c) emtricitabine-triphosphate (FTC-TP) concentrations (recent adherence measure) in transgender persons of all adherence levels taking versus not taking hormones. These analyses will be analogous to the descriptive analyses in the primary outcomes. For FAAB transgender individuals, to determine the change between baseline and week 12 testosterone levels in individuals taking PrEP and receiving stable testosterone replacement (controlling for route, dose and formulation), we will use a paired test. For hormone therapy satisfaction, the main outcome of interest to these individuals is maintaining the physically desirable characteristics that the csHT provide. Thus, it is not the hormone levels that are as important

as the satisfaction with these traits. For the entire cohort of MAAB who are on stable csHT dosing (as defined as no change from baseline to week 12) from baseline to week 12 and from baseline to week 48 we will compare the hormone satisfaction with physical traits ranked for satisfaction using the BIS and summed for overall satisfaction score to compare between weeks 0, 12 and 48. Similarly, we will use the BIS for FAAB on stable csHT assessing physical traits compared at weeks 0, 12 and 48.

SUB-STUDY IV PROCEDURES

At Baseline, eligible participants will consent for additional sub-study sample collection on the main study informed consent form. Genital collection for *Neisseria gonorrhoeae* and *C. trachomatis* will be done at Baseline and Week 24 as part of the main study STI screening procedures.

For the sub-study, two genital swabs for microbiome and cytokine testing will be collected at Baseline and Week 24. Additional genital swabs for a vaginitis multiplex assay, herpesvirus and HPV testing as well as CVF collection via aspirator for TFV levels will be collected at Week 24.

Sub-study IV	Study Weeks of Follow-up					
Schedule of Evaluations	Screen	Wk 0	Wk 24			
Window	14 days	30 days	+/- 4 weeks			
Informed Consent	Х					
CV swab for cytokine testing		Х	Х			
CV Swab for microbiome		Х	X			
CVF collection for drug concentration TFV			X			

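### Sub-study I's secondary comparisons of drug levels by hormone or antiandrogen use do not name adherence as a covariate, and the aims and the analysis plan disagree on whether the hormone comparison is adjusted at all

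*Combined protocol and SAP*

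**What the plan says.** Section 6, Sub-study I Secondary Objectives, sets three comparisons of drug level by exposure.

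- Objective 2 is TFV-DP by cross-sex hormone therapy (csHT) in participants assigned male at birth (MAAB): "To determine TFV-DP in MAAB of all adherence levels compared to not taking csHT, adjusting for confounding factors". The confounding factors are not listed.
- Objective 3 is TFV-DP by antiandrogen use in MAAB. No adjustment is stated.
- Objective 5 is FTC-TP "in TG / GNC persons of all adherence levels taking versus not taking hormones". No adjustment is stated.

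Section 9, Sub-study Statistical Considerations, Analysis Plan, introduces the same three as potential interactions:

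- "a) TFV-DP in transgender persons (MAAB and FAAB) of all adherence levels compared to not taking csHT"
- the antiandrogen contrast on TFV-DP, again in MAAB, with no restriction or covariate named
- FTC-TP "concentrations (recent adherence measure) in transgender persons of all adherence levels taking versus not taking hormones"

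The only method given for them is "These analyses will be analogous to the descriptive analyses in the primary outcomes". The sub-study's primary outcome is a continuous drug level, compared by a two-sample t-test with means, SDs and confidence intervals.

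A regression is planned as a secondary or sensitivity analysis of that primary comparison with existing MSM data. Its candidates are "clinical and demographic factors (age, race, ethnicity, education, socioeconomic status, sexual risk behaviors, substance use, depression, concomitant medications". A variable enters only if it is associated with both group and outcome at p<0.10.

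Daily iTAB text responses are collected as the self-reported adherence measure (Sub-study I Procedures).

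**The concern.** Participants choose whether to take hormones; they are not randomised to them. Doses taken are a main determinant of the drug level. If users and non-users differ in dosing, an unadjusted contrast mixes that difference with any pharmacokinetic effect. Lower dosing in users would look like an interaction. Higher dosing in users could cancel a real one.

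The protocol raises this ambiguity itself. Section 7, on the interaction of hormones and TDF/FTC, says of an earlier open-label study that "transgender subjects had 30% lower levels of TFV-DP for reasons that were not determined but could be from poorer adherence, different pharmacokinetics or both". An unadjusted comparison across all adherence levels cannot separate those explanations. The FTC-TP contrast is the most exposed, because the plan calls FTC-TP a measure of recent adherence.

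The interaction question matters to this population: the background cites concern about hormone efficacy as a possible barrier to PrEP.

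**Working it through.** **1. Aims against analysis plan.**

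| Comparison | Section 6 | Section 9, Analysis Plan |
|---|---|---|
| TFV-DP by csHT | MAAB; adjusted, factors unnamed | MAAB and FAAB (assigned female at birth); descriptive |
| TFV-DP by antiandrogens | MAAB; no adjustment stated | MAAB; descriptive |
| FTC-TP by hormones | All; no adjustment stated | All; descriptive |

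The first row conflicts on both population and method. No row names adherence.

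**2. The plan's own figure.** The only Sub-study I sample size is 45, for the primary non-inferiority test. With SD 350, margin 230, assumed shortfall 100, one-sided 5% and 80% power:

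n = [350 × (1.645 + 0.842) / (230 − 100)]² = 44.8, rounded up to 45.

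It reproduces. It applies to perfect adherers; no figure is given for the three secondary comparisons.

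**3. Inputs for the illustration.**

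- Group sizes: 196 MAAB on feminizing hormones and 84 on none (Sample Size and Power).
- Level per weekly dose: 1560 / 7 = 222.9 fmol/punch, from the daily-dosing level of 1560. The plan itself equates one tablet a week with 230.
- SD: 350 (planning value) and 694 (observed in 37 MSM reporting perfect adherence, Section 7, Preliminary Data).
- Assumptions not in the documents: the dosing gap (0.25 to 1 dose a week), no true hormone effect, and every participant contributing a level.

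**4. Bias and false-positive rate.**

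Bias = gap × 222.9.

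SE = SD × √(1/196 + 1/84) = SD × 0.1304, which is 45.6 at SD 350 and 90.5 at SD 694.

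P(significant, two-sided 5%) = Φ(bias/SE − 1.96) + Φ(−bias/SE − 1.96).

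| Assumed gap (doses/week) | Bias (fmol/punch) | SD 350 | SD 694 |
|---|---|---|---|
| 0.25 | 56 | 23% | 9% |
| 0.5 | 111 | 68% | 23% |
| 1 | 223 | >99% | 69% |

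At 230 per weekly dose, the 0.5-dose row becomes 115 fmol/punch, 71% and 25%.

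**5. Masking.** Take a true reduction of 230 with users taking one more dose a week. At 230 per weekly dose the expected difference is 230 − 230 = 0. The chance of a significant result falls to 5%, from over 99% (SD 350) or 72% (SD 694) with no dosing gap.

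**6. Sensitivity to the SD.** Both SDs describe perfect adherers. Suppose weekly doses vary between people with SD 2 (an assumption). The total SD is √(350² + (2 × 222.9)²) = 567, the SE is 73.9, and the 0.5-dose rate is about 33%. The bias stays at 111.

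**The case against.** Several points on the other side stand.

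- **Adjustment is not wholly absent.** A reader of the Analysis Plan alone might infer that the hormone comparison is meant to be unadjusted. Objective 2 says otherwise. For that comparison the fault is a conflict between sections and unnamed confounders. Only the other two have no stated adjustment.
- **The primary hypothesis already controls adherence.** A reader might infer that the sub-study's main conclusion is confounded by dosing in the same way. The documents do not support that: the primary hypothesis is limited to MAAB participants on csHT with perfect iTAB-reported adherence over 34 days.
- **The covariate list is weak evidence of an oversight.** It belongs to that primary comparison, where adherence is already fixed by restriction. What matters is that nothing replaces the restriction in the secondary comparisons.
- **These analyses are exploratory and the section is brief.** The protocol defers detail to a formal SAP, due before database lock, that takes precedence. That lowers the severity. It does not settle the matter, because the method that is stated is the confounded one.
- **The FTC-TP contrast could be meant as a check on recent dosing.** That is possible, but the plan lists it among potential interactions.
- **The percentages are conditional.** The counts are MAAB only, while the Analysis Plan also includes FAAB in the hormone comparison, and no split by antiandrogen use is given. Blood spots are not collected from participants off study medication, so 196 and 84 are upper limits.

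**Conclusion.** The concern holds in a limited form. Section 6 and the Analysis Plan disagree on the csHT comparison, and adherence is named as a covariate for none of the three. Followed as written in the Analysis Plan, these contrasts cannot distinguish a dosing difference from a drug interaction, in either direction.

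The size depends on a dosing gap the documents do not give. At an assumed 0.5 dose a week the bias is about 111 fmol/punch, nearly half of what the plan treats as one tablet a week. The 68% and 23% illustrate that case. They should not be read as the trial's expected error rate: they assume complete data and SDs from perfect adherers, and a larger SD would lower them without reducing the bias.

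This is a cheap improvement to secondary analyses.

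**What to change.** 1. Align Section 6 and the Analysis Plan on the population (MAAB only, or MAAB and FAAB) and on adjustment for the csHT comparison.
2. For all three comparisons, make the main analysis a regression of drug level on hormone (or antiandrogen) status. Include iTAB-reported dosing in a fixed window before the blood spot as a mandatory covariate, exempt from the p<0.10 screen. Use 34 days for TFV-DP, as in the primary hypothesis. For FTC-TP pre-specify a shorter window; the documents give no length.
3. Add randomised arm and the covariates already listed, excluding the exposure under test. Concomitant medications need care, because that review at study visits includes csHT use.
4. Report the adjusted difference, or the ratio if levels are logged, with its 95% CI. Do not apply the 230 margin: it is an absolute difference set for perfect adherers near 1560. Keep the unadjusted figure as descriptive.
5. Add a sensitivity analysis treating iTAB non-response as missing. Under Adherence and Behavioral Assessments, non-response counts as a missed dose, so the covariate partly measures reply behaviour. If replying differs by hormone use, adjustment could itself add bias.

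The cost is wording in the SAP, since the text data are already collected. Text reports are imperfect, so residual confounding will remain and should be stated with the results.

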For participants with disqualifying safety laboratory results, the study coordinator will instruct the participant to immediately cease study medication and an interim screen failure visit will be scheduled at the clinic. The following procedures will be conducted at the screen failure visit:

- Participant will return any remaining study medications.
- Participants with disqualifying creatinine or creatinine clearance values may request to re-screen into the study but may not repeat a same-day PrEP initiation visit.
- If HBsAg positive, the participant will be referred to care.
- If HIV positive, study coordinators will follow the procedures outlined in 6.11.4 and 6.11.5 in the Protocol.
- Participant will be terminated from the study as a Screen Failure.

In-Clinic Study Visits (Weeks 12, 24, 36, and 48; approximately 1 hour)

Participants will be asked to return to the clinic at week 12 and every 12 weeks up to week 48. Study visit procedures include:

- Assessment of adverse events since last contact.
- Targeted medical history and physical examination, including collecting weight
- Review of concomitant medications, including detailed csHT use
- Laboratory evaluations
 - Rapid HIV screening
 - 3-site (throat, rectal, urine) STI NAAT screening for gonorrhea and chlamydia (weeks 24 and 48 only)
 - Syphilis RPR (weeks 24 and 48 only)
 - Calculated creatinine clearance (Cockcroft-Gault)
 - Plasma hormone levels for participants on csHT (week 12 only, sub-study only)
 - Urine β-HCG for participants capable of being pregnant.
- Sample collection for banking
 - Dried blood spot (DBS) for participants on PrEP
 - Whole blood, plasma, and serum
 - Urine
 - Rectal swabs (week 48 only)
- CASI assessments
- Medication dispensation. Participants will be provided enough medication to last until the next scheduled visit through the investigational pharmacy. Participants will not be provided PrEP at week 48.
- Risk reduction and medication adherence counseling. Counseling will not be performed at week 48.
- End of Study assessment (week 48 only). This survey will assess participant's experiences over the course of the study, including changes in their medical insurance status, access to other healthcare services, changes in perceptions of PrEP and of their own health, and their opinions about the intervention.

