Vaginal swab for herpesvirus and HPV			X			
Vaginal swab for vaginitis multicomplex			X			

Sub-study IV Statistical Considerations

Aim 1: To determine the impact of pro-inflammatory STIs on CVF TFV levels.

We will quantify CVF TFV levels of participants at week 24 and compare levels in those with and without the presence of active vaginal infections using methods for continuous measures (i.e., the Student t test or Wilcoxon test depending on distributions). The primary analysis will compare those with any infection to those with no detected infection. We will examine individual organisms in subanalysis. We will also compare the proportion of participants with TFV levels in steady state (\geq 50 ng/mL) to those with levels that are not (<50 ng/mL) at week 24 for vaginal infections using Fisher's exact test. The threshold of \geq 50 ng/mL was selected based on previously reported CVF steady state trough concentrations at 24 hours achieved by oral dosing (\leq 11).

Sample Size: Based on an estimated mean concentration of 119 ng/mL and a standard deviation of 58 ng/mL in CVF TFV in a steady state PK study(32), we have 80% power with a one-sided lower bound alpha of 0.05 to detect a difference in individuals with STIs versus those without STIs of 33 ng/mL or 28% reduction in CVF TFV levels in a sample of n=40.

Aim 2: To determine the impact of CV inflammation on CVF TFV levels.

We will compare TFV levels as a continuous measure with \log_{10} -transformed cytokine levels at week 24 using the Pearson correlation test or Spearman correlation test if they are not normally distributed. For assessment of chronic inflammation and TFV levels, we will compare those with and without elevated cytokine levels of at least one cytokine (MIP-1 α and β , IP-10, IL-6 and IL-8) that remains higher at both baseline and week 24 using Student t-test or Wilcoxon depending on distributions. If cytokine levels are below the level of detection in \geq 40% of samples, these will be converted to categorical variables (detectable versus undetectable).

Exploratory Aim: To assess the impact of the CV microbiome on CVF TFV levels.

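### Sub-study IV relates week-24 cervicovaginal tenofovir to infection and cytokine status with no account of adherence, so a dosing difference between groups could mimic or mask a biological effect.

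*Combined protocol and SAP*

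**What the plan says.** The analysis is in Section 9 of the combined protocol and SAP, under Sub-study IV Statistical Considerations. Aim 1 will "compare levels in those with and without the presence of active vaginal infections using methods for continuous measures", meaning a t-test or a Wilcoxon test. On the main contrast it states: "The primary analysis will compare those with any infection to those with no detected infection". A second analysis splits CVF TFV at 50 ng/mL and compares proportions "at week 24 for vaginal infections using Fisher's exact test". Aim 2 uses Pearson or Spearman correlations with log cytokines, and a two-group test for persistently raised cytokines. The microbiome aim is exploratory and largely descriptive. None of these names drug levels in dried blood spots (DBS), text-reported doses or time since last dose as a covariate, stratifier or restriction.

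Other parts of the document bear on this:

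- Section 7, Sub-study IV Background, presents the sub-study as a search for biological explanations other than adherence.
- Section 7, Study Background, reports that in the earlier text-message study only half of those on PrEP had perfect adherence at week 48.
- Section 9, In-Clinic Study Visits, lists "Dried blood spot (DBS) for participants on PrEP" at week 24, among the samples for banking. Participants who stay on study but off medication have no DBS taken, and their text account is made inactive.
- Section 6, secondary objective 2d, needs drug levels at every attended visit, so a week-24 TFV-DP result is implied.
- Section 9, Adherence and Behavioral Assessments, describes daily text-reported dosing.
- FTC-TP appears only in Sub-study I. The objective in Section 6 begins "To determine emtricitabine-triphosphate (FTC-TP) concentrations (a measure of recent adherence", and no week-24 assay is fixed for Sub-study IV participants.

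**The concern.** Participants with and without an infection are observed groups. They may differ in how regularly they take the drug, and CVF TFV can be expected to depend on dosing. The trial's own list of candidate causes of poor adherence (Section 6, objective 5) includes substance use, partner violence, socioeconomic status and perceived risk, which could also track with exposure to infection.

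Elsewhere the document treats adherence as a rival explanation for drug levels. Section 7 says that the lower TFV-DP seen in transgender participants of an earlier study might reflect adherence, pharmacokinetics or both. Sub-study I restricts its primary hypothesis to people reporting perfect adherence over 34 days. Sub-study IV asks a similar kind of question without such a safeguard.

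The 50 ng/mL split is also exposed. That threshold comes from steady-state troughs 24 hours after oral dosing, so a value below it may mean a missed dose rather than an effect of infection. At stake is whether the sub-study can say anything about biology apart from pill-taking.

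**Working it through.** **1. The plan's own figure.** Inputs from Aim 1: "estimated mean concentration of 119 ng/mL", "standard deviation of 58 ng/mL in CVF TFV in a steady state PK study", a difference of 33 ng/mL (33/119 = 27.7%, matching the stated 28%), and "we have 80% power with a one-sided lower bound alpha of 0.05", with n=40.

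n per group = 2 × (1.645 + 0.842)² × 58² / 33² = 38.2, so 39. With 40 per group the power is 81.6%, so the figure reproduces as 40 per group. With 40 in total (20+20) it is 56.1%. Section 10 offers the sub-study to 20 people plus a few with neovaginas; at 10+10 the power is 35.5%. The mismatch between 20 and 40 is a separate matter, but it limits how many covariates are realistic.

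**2. What a gap in recent dosing could produce.** Assumptions, none from the documents except the 119: recent dosers average 119 ng/mL, non-dosers about 0, infection has no effect, and the stated proportions have dosed recently.

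Spurious difference = 119 × (proportion dosing, uninfected − proportion dosing, infected)

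- 90% v 80%: 119 × 0.10 = 11.9 ng/mL; 11.9/33 = 36% of the target
- 90% v 70%: 119 × 0.20 = 23.8 ng/mL; 23.8/33 = 72% of the target

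If the infected group doses more, the same amounts are added to its mean and mask a true reduction.

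**3. The same question in doses per week.** Assume CVF TFV is proportional to weekly doses (119/7 = 17 ng/mL per dose), the total SD is 58, and there is no infection effect. The chance that the one-sided 5% t-test declares a reduction is:

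| Infected group takes fewer doses/week by | Spurious difference | 10+10 | 20+20 | 40+40 |
|---|---|---|---|---|
| 0 | 0 | 5% | 5% | 5% |
| 1 | 17 ng/mL | 15.5% | 23.1% | 36.5% |
| 2 | 34 ng/mL | 35.1% | 57.0% | 83.0% |

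A gap of 33/17 = 1.94 doses per week would reproduce the whole target difference.

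**4. What one covariate recovers.** The step 3 model was simulated with a within-group SD of 1.5 doses per week, so the residual SD is √(58² − (17 × 1.5)²) = 52.1. Adjusting for a perfectly measured adherence covariate returns the false-positive rate to 5.1–5.5% and the bias to about 0. A covariate with reliability 0.7 leaves about 5 ng/mL of bias and a rate of 7–11% for a one-dose gap, or about 10 ng/mL and 10–18% for a two-dose gap.

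**5. Which covariate.** Section 6 equates 34 days with two TFV-DP half-lives, so the half-life is 17 days. Under simple exponential decline, a person at 1246 fmol/punch who stops dosing falls to 719 only after 17 × log₂(1246/719) = 13.5 days. TFV-DP at or above 719 therefore does not show that doses were taken in the last few days. Text-reported doses before the visit are closer to recent dosing, but a non-reply counts as a missed dose, so they are also imperfect.

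**The case against.** The strongest case against has four parts.

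- **No documented link.** Nothing in the documents ties infection to adherence in either direction, and the dosing gaps above are invented for illustration. That stands. It limits any statement of size but does not remove the exposure, since the groups are observational and adherence is expected to vary. It is also fair that in a 10+10 split, 9 v 7 recent dosers is a difference of two people; a chance imbalance of that kind is sampling variation the test already allows for. The concern is with a systematic gap.
- **Over-adjustment.** Section 7 says inflammation may affect intracellular TFV, so adjusting for DBS TFV-DP might remove part of the effect under study. This is weak. The text does not say that genital inflammation changes blood-spot levels, text-reported doses would not be open to it in the same way, and showing the unadjusted test alongside lets the reader see the difference.
- **Small sample.** About 20 participants will not support two correlated covariates plus a restricted subset. That stands, and it is why a single covariate is the sensible limit.
- **A fuller SAP is promised.** Section 9 says so and gives it precedence. Nothing supplied shows that it will include this adjustment, so it is the place for the remedy rather than an answer to the point.

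**Conclusion.** The point holds. As written, Aims 1 and 2 cannot separate an infection or inflammation effect from a difference in dosing. Under the stated assumptions, recent-dosing gaps of 10 to 20 percentage points amount to 12 to 24 ng/mL, or 36% to 72% of the target difference, with no infection effect. The direction of any bias is unknown.

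Three stronger readings are tempting but unsupported:

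- **That Aim 1 will report a false infection effect.** The documents contain no estimate of the adherence–infection link, and the bias could equally hide a true reduction.
- **That every adherence marker is already in hand at week 24.** DBS is collected only from those on PrEP, TFV-DP at that visit is implied by objective 2d, and FTC-TP is not fixed as a week-24 assay for these participants.
- **That adjustment would let a difference be attributed to infection.** A small observational comparison with an imperfect covariate will leave some confounding.

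For the exploratory microbiome aim the point carries little weight. Overall this is a correction worth making before the SAP is final; it does not invalidate the sub-study.

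**What to change.** In the SAP, prespecify one adherence-adjusted analysis for Aim 1: a linear regression of (log) CVF TFV on any infection with one adherence covariate. Choose the covariate in advance from data the trial already collects, either text-reported doses over a stated recent period before the week-24 visit or week-24 DBS TFV-DP. For Aim 2, specify the partial correlation with the same covariate. Report the planned unadjusted tests beside both.

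State how participants off drug at week 24 are analysed, since they have no DBS and an inactive text account. One option is to exclude them from this analysis of drug levels and report their number by infection status. Use FTC-TP only if it is actually assayed at week 24. Word the results as associations.

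The cost is SAP text and one degree of freedom in about 20 participants. No new visit or sample is needed. Text-reported doses need no assay, and the TFV-DP result is one that objective 2d already requires. Residual confounding may remain.
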